5.1 General Methodology

All statistical analyses will be conducted using SAS v9.4 or later version on the Microsoft Windows Operating System.

All eCRF data (raw data) will be converted into SDTM (Study Data Tabulation Model) datasets, which will be used to create ADaM (Analysis Data Model) data sets. The creation of the SDTM and ADaM data sets will follow the CDISC (Clinical Data Interchange Standards Consortium) standards and the FDA Study Data Technical Conformance Guide. All analysis tables and listings will be created from the ADaM data sets.

Continuous data will be summarized using "n" (number of subjects with non-missing observations), mean, median, standard deviation (SD), minimum value, and maximum value. Categorical data will be summarized using the frequency count and percentage (n, %) of subjects in each category. Number of subjects with non-missing values or number of subjects with missing values (e.g., Not Done) will be presented, where appropriate. Subjects with missing values will not contribute to the denominator for percentage calculations, unless specified otherwise. Counts of 0 in any category will be presented without percentage. All summaries will be presented for individual treatment groups. In Allakos Inc. Page 24 of 49 *Confidential* addition, for summary of disposition and subject baseline characteristics, the presentation will include both treatment groups combined.

The precision rules for the presentation of summary statistics will be:

- Sample size (n, N) and number of missing responses (if displayed): Integer
- Mean, confidence interval, and median: Same number of decimal places as reported/collected
- Standard deviation: Same number of decimal places as reported/collected
- Percentiles, minimum, maximum: Same number of decimal places as reported/collected
- Odds Ratio: 2 decimal places
- Percentage: 1 decimal place generally, or 2 decimal places for <0.1%, or no decimal places for 0% and ≥100%
- P-value: 4 decimal places
- WBC: 2 decimal places as $0.01 \times 10^9/L$
- Height/Weight/BMI: 1 decimal place

The data summaries will be accompanied by individual subject data listings. All data available from questionnaires, eCRF, and external transfer (labs) will be listed and will include relevant subject information, e.g., treatment group and study day. The listings will be sorted in the order of treatment group, subject ID, assessment name and date/time.

Dates will be presented in the ISO-8601 format YYYY-MM-DD. Times will be displayed in 24-hour clock format. Numbering for tables, figures and listings will follow ICH E3 Guideline (ICH, 1996).

Alternative methods of analysis of the data may be considered prior to database lock, and reason for departure from the planned methods will be documented in an amendment to the SAP or in the CSR.

5.2 Visit Window and Unscheduled Assessments

Data collected for study assessments provide information on the status of the subject at a given time point. For all the non-daily, by-visit assessments, no analysis window will be defined. The by-visit summaries will be performed based on their associated visits.

In the event of multiple values from unscheduled or early termination assessments associated with a single visit, the value closest to the scheduled visit target study day will be used for analyses. If 2 values tie as closest to the time point (for example, 1 value is before and the other value is after the

time point), then the later value will be selected. Data collected at all visits will be included in the data listings with visit presented as reported by the site.

Post-baseline weekly diary endpoints will be derived from subject daily diary windows anchored on day of first dose (Study Day 1) and day of last dose. Weeks 1 through 9 are defined in Table 8.

Analysis Week	Study Days
1	1 – 7
2	8-14
3	15 - 21
4	22 - 28
5	29-35
6	36 - 42
7	43 - 49
8	50 - 56
9	57 - 63

 Table 8
 Analysis Week Definitions Based on Scheduled Visits

The diary window of Week 12 is the 7 days prior to the earlier of a) 14 days after Day 71 dose; or b) Open Label Extension Day 1 dose. In the case of diary non-compliance (fewer than 4 completed daily diaries in the Week 12 diary window), the start of the window can be extended back one day at a time until 4 completed daily diaries are obtained, or up to the day of Day 71 dose, whichever is reached first. If the Week 12 diary window still has fewer than 4 daily diaries after extending the start of Week 12 diary window to the day of Day 71 dose, the Week 12 diary window is defined as 7 days and the value of the window is set to missing.

The Week 11 diary window begins on the day of Day 71 dose and ends on the earlier of a) six days after Day 71 dose; or b) 1 day prior to the start of the Week 12 diary window.

The diary window of Week 10 begins on the latter of a) 7 days prior to Day 71 dose; or b) Study Day 64 and ends on the day before Day 71 dose.

If after constructing the diary windows there are fewer than 4 completed daily diaries for any week, the value of that week is set to missing and subject to imputation rules.

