10.1 Formulation of Test Product and Placebo

Note: Lirentelimab SC and placebo SC will be referred to as "study drug."

Each dose (lirentelimab SC or placebo SC) will comprise 1 SC injection of 2 mL of study drug administered in the front of the thigh with a 27-gauge SC needle. Maximum volume administered will be 2 mL. Lirentelimab SC or placebo SC (based on randomization assignment)

will be administered on Day 1 (±3), Dose 1; Day 15 (±5), Dose 2; Day 29 (±5), Dose 3; Day 43 (±5), Dose 4; Day 57 (±5), Dose 5; and Day 71 (±5), Dose 6.

Subjects will have the option to enroll in an OLE period to receive 6 doses of 300 mg lirentelimab SC. Subjects will be observed for at least 1 hour after each injection.

Dosing visits must be conducted within the \pm windows stipulated in the protocol with the following requirements:

- The interval between dosing visits must be at least 7 days and no more than 21 days from the previous dosing visit unless directed otherwise by Allakos. The interval count starts the day after the visit and includes the day of the next visit.
- The interval between the final dosing visit and the efficacy visit (Day 85) must be at least 11 days and no more than 17 days from the final dosing visit unless directed otherwise by Allakos. The interval count starts the day after the visit and includes the day of the next visit.

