2.1.1 Weekly Urticaria Assessment Score (UAS7)

The UAS7 is the sum for 7 days of the daily Hives Severity Score (HSS) and the daily Itch Severity Score (ISS). The possible range of the weekly UAS7 score is 0–42. Complete UAS7 response is defined as UAS7 = 0 or by reduction of \geq 90% from baseline.

The severity of hives will be recorded by all subjects once daily in their Urticaria Patient Daily Diary (UPDD), on a scale of 0 (none) to 3 (> 50 hives) (see Table 1). A weekly HSS score (HSS7) is derived by adding the average daily scores of the 7 days preceding the visit. Therefore, the possible range of the weekly score is 0 - 21. A complete hives response is defined as HSS7 = 0. When one or more of the daily scores are missing, the following principles will be applied to handle the missing data:

- At baseline and post-baseline time points, if a subject has at least 4 non-missing daily scores within a given week, the weekly score is calculated as the sum of the available scores in that week, divided by the number of days that have a non-missing diary score, multiplied by 7.
- At post-baseline time points, if there are less than 4 non-missing daily scores within a given week, then the weekly score is set to missing. Missing data will be imputed using methods outlined in Section 6.9.1. It is worth remarking that missing data imputation is not required at baseline since a minimum of 4 daily scores per week are required to determine subject eligibility for the study.

Score	Number of Hives per 24 Hours
0	None
1	< 20
2	20-50
3	> 50

Table 1Hives Severity Score

The severity of itching will be recorded by all subjects once daily in their UPDD, on a scale of 0 (none) to 3 (severe) (see Table 2). A weekly ISS score (ISS7) is derived by adding the average daily scores of the 7 days preceding the visit. Therefore, the possible range of the weekly score is 0 - 21. Partially missing diary entries will be handled in the same way described for the hives severity score.

A complete itch response is defined as ISS7 = 0.

Score	Pruritus (Itch) over the last 24 Hours		
0	None		
1 Mild (present but not annoying or troublesome)			
2	Moderate (troublesome but does not interfere with normal daily activity or sleep)		
3	Severe (severe itching, which is sufficiently troublesome to interfere with normal daily activity or sleep)		

Table 2Itch Severity Score

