4.1 Terminology and Definitions

Terminology	Definition
Baseline	Baseline for non-daily assessment (e.g., laboratory tests) is defined as the non-missing value collected most recently to and before the time of the very first dose of study drug. Baseline Patient Reported Outcome (PRO) data will be the average or the sum of the weekly PRO data collected in the last 7 days prior to Day 1 depending on the outcome under consideration.
Concomitant Medications and Procedures	Medications and procedures with a stop date before the treatment dosing date will be considered prior medications/procedures. Medications and procedures with a start or stop date on or after the treatment dosing date will be considered concomitant. All medications/procedures marked as ongoing are concomitant.
Study Day	Study Day 1 is defined as the date on which a subject received the first dose of study drug. For visits prior to the first dose of study drug, Study Day is calculated as Visit Date – Day 1 Date. For visits after the first dose, Study Day is calculated as Visit Date – Day 1 Date +1.
Study Week	Study Week for PRO analysis is defined as 7 days a week starting from the day of first dose (Day 1). Details are provided in Section 5.2.

Table 7Terminology and Definitions

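### SAP 5.2 makes the Week 10 diary window too short to score when Dose 6 is given on Day 66 or 67, so Week 10 is missing even with a complete diary

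*SAP*

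**What the plan says.** SAP 5.2 builds the weekly diary windows from two anchors, the first dose and the last dose. Weeks 1 to 9 are fixed blocks of seven study days, and Table 8 puts Week 9 at Days 57–63. Weeks 10 to 12 are placed around Dose 6.

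For Week 10 the rule is: "The diary window of Week 10 begins on the latter of a) 7 days prior to Day 71 dose; or b) Study Day 64". The window closes the day before Dose 6 ("Study Day 64 and ends on the day before Day 71 dose").

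The minimum content of a week appears twice. SAP 5.2 says that where there are "fewer than 4 completed daily diaries for any week, the value of that week is set to missing and subject to imputation rules". SAP 2.1.1 has the same threshold for the score: "if there are less than 4 non-missing daily scores within a given week, then the weekly score is set to missing".

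Protocol 10.1 gives the dosing windows ("Day 57 (±5), Dose 5; and Day 71 (±5), Dose 6") and the spacing rule: "The interval between dosing visits must be at least 7 days and no more than 21 days from the previous dosing visit". SAP 4.1 fixes the origin of the count: "Study Day 1 is defined as the date on which a subject received the first dose of study drug".

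Week 12 has a relief rule in SAP 5.2: when diaries are short, its start may move back towards the day of Dose 6, and Week 11 is cut to end the day before Week 12 begins. Week 10 has no such rule.

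**The concern.** A weekly value should be missing because the subject did not fill in the diary. Here it can be missing only because a visit took place early in its permitted window. Week 10 cannot start before Day 64 and must stop the day before Dose 6, so an early Dose 6 squeezes it from both ends, and SAP 5.2 guarantees it no minimum length.

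The lost value matters in three places:

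- **Primary multiple imputation (SAP 6.9.1).** The imputation variables run from Visit0 to Visit12. A blank Week 10 between observed weeks is an artificial intermittent gap. If Weeks 11 and 12 are also missing after an intercurrent event, the last week before Dose 6 is imputed instead of observed.
- **HSS7 and ISS7 mixed models (SAP 6.9.2).** Week is a repeated categorical factor, with estimates at each time point.
- **Figures 1–3.** These plot UAS7, HSS7 and ISS7 over time, and n falls at Week 10.

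**Working it through.** **Inputs**

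- Dose 6 day D: 71 ± 5, so 66 to 76 (Protocol 10.1).
- Dose 5 day: 57 ± 5, so 52 to 62 (Protocol 10.1).
- Interval between dosing visits: 7 to 21 days (Protocol 10.1).
- Week 10 start: max(D − 7, 64). Week 10 end: D − 1 (SAP 5.2).
- Minimum for a weekly value: 4 diaries (SAP 5.2 and 2.1.1).

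**Formula.** Length of Week 10 = (D − 1) − max(D − 7, 64) + 1 = D − max(D − 7, 64).

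**Check on the nominal schedule.** D = 71 gives Days 64–70, which is 7 days, so the rule works as intended there.

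**All allowed Dose 6 days**

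| Dose 6 day | Week 10 window | Days available | Week 10 value with a complete diary |
|---|---|---|---|
| 66 | 64–65 | 2 | missing |
| 67 | 64–66 | 3 | missing |
| 68 | 64–67 | 4 | present, lost with one missed diary |
| 69 | 64–68 | 5 | present |
| 70 | 64–69 | 6 | present |
| 71 to 76 | D − 7 to D − 1 | 7 | present |

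**Are Days 66 and 67 reachable under the interval rule?** For D = 66, Dose 5 on Days 52–59 gives intervals of 14 down to 7 days. For D = 67, Dose 5 on Days 52–60 gives 15 down to 7 days. Both are allowed without a deviation.

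**Is Week 12 affected?** With no earlier open-label dose, Week 12 runs from D + 7 to D + 13: Days 73–79 for D = 66 and Days 74–80 for D = 67. It is a full week placed from Dose 6, so this rule does not touch it.

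**How many subjects?** The documents give no distribution of actual Dose 6 days, so a share has to be assumed. At 5% of the 130 planned subjects, 0.05 × 130 = 6.5. Not all 130 will reach Dose 6. With the planned dropout of about 10%, 0.9 × 130 = 117 and 0.05 × 117 = 5.85, about 6.

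**Effect of letting Week 10 borrow from Week 9, with complete diaries**

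- D = 66: Week 10 becomes Days 62–65 (4 days) and Week 9 becomes Days 57–61 (5 days). Two days move.
- D = 67: Week 10 becomes Days 63–66 (4 days) and Week 9 becomes Days 57–62 (6 days). One day moves.

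Both weeks then reach four diaries, and no day is counted twice.

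**The case against.** The best defence is that the Day 64 floor looks deliberate. With two anchors and seven-day weeks that do not overlap, an early Dose 6 must leave one short week, and the floor stops Week 9 days from being counted again in Week 10. Back-extension is also reserved for Week 12, the endpoint week; Weeks 1–9 and 11 do not have it either. And every endpoint legible in the documents that is built on UAS7, HSS7 or ISS7 is read at Week 12.

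Most of this stands, and it limits the harm. It does not remove the defect. Weeks 1–9 are always seven days long and need no relief, whereas Week 10 can fall below four days on a schedule the protocol permits. A floor against double counting does not require losing the week, because days can be moved instead of shared.

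Four stronger readings may tempt a reader, and the documents do not support them:

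- *A fully recorded week is thrown away.* It is not. For D = 66 the unused days are 64 and 65, and for D = 67 they are 64 to 66. Days 57–63 still count in Week 9, and Week 11 starts on the day of Dose 6.
- *The Week 10 point in the figures is biased.* The missingness follows the visit date in a blinded trial, and nothing in the documents links that date to arm or outcome. What is lost is precision.
- *About 18% of subjects are affected, as 2 of the 11 allowed days.* That needs Dose 6 to be spread evenly over a window centred on Day 71. The documents give no basis for that, and visits aimed at Day 71 make it implausible.
- *A late Dose 6 is an equal problem.* With Dose 6 on Days 72–76, between 1 and 5 diary days from Day 64 onward belong to no week. Week 10 is still a full seven days, so no weekly value becomes missing.

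**Conclusion.** The point holds as a small, certain defect in a derivation rule. For Dose 6 on Day 66 or 67, Week 10 is missing by construction; on Day 68 it is missing after a single skipped diary. No other rule in either document rescues it.

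The consequence is avoidable missing data at one intermediate week. For a subject with an observed Week 12, an imputed Week 10 does not enter that subject's change score, so the primary estimate should move little. A direct effect on an imputed Week 12 needs both an early Dose 6 and a missing Week 12 value, and Week 9 is still there to inform it. The HSS7 and ISS7 models lose some observations at Week 10.

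The window arithmetic needs no assumption beyond the stated windows. The count of 6 or 7 subjects rests wholly on an assumed 5% dosed on Days 66–67.

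**What to change.** Amend SAP 5.2 as follows before database lock; SAP 5.1 allows documented changes up to then.

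1. If Week 10 holds fewer than four completed diaries, move its start earlier by single days until it holds four.
2. Set two limits: the start may not fall earlier than 7 days before Dose 6, and Week 9 must keep at least four completed diaries.
3. Week 9 then ends the day before Week 10 starts, as Week 11 already yields to Week 12.
4. If four diaries cannot be reached within these limits, leave both windows as now defined and set Week 10 to missing.

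The first limit confines the change to Dose 6 on Days 66–70, since from Day 71 onward the window already starts 7 days before the dose.

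The cost is a few lines of text, a change to one derivation and a footnote to Table 8. With complete diaries, Week 9 is prorated from 5 days (Dose 6 on Day 66) or 6 days (Day 67) instead of 7. That is a modest loss of precision in Week 9 in exchange for an observed Week 10. Late doses on Days 72–76 need no change.

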5.3 Adjustment for Covariates

Efficacy analyses will be adjusted for baseline values and randomization strata using ANCOVA, MMRM, or Cochran-Mantel-Haenszel tests, where applicable.

5.4 Data Handling Conventions

This section includes the methods for missing data imputation for some summary analyses, if necessary.

Adverse events with incomplete start or stop dates (i.e., either day or month is missing) will be considered treatment-emergent adverse events (TEAE) unless the partial start date or the stop date confirms the AE started or ended prior to Study Day 1 (e.g., the day of the AE start date is unknown but the month and year indicate that the AE starts prior to Study Day 1). Adverse events with missing relationship to study drug will be included in the "Related" category for the summary tables and footnoted. Adverse events with missing severity will not be included in the by-severity summary table but will be footnoted in the table.

When there is incomplete information regarding dosing dates for prior and concomitant medication, the medication will be considered as a concomitant medication unless it contradicts with the stop date. For example, a medication will be considered a prior medication if the month and year of the end date indicates a date before Study Day 1 even though the start date could be missing.

5.5 Independent Safety Monitoring Committee

An independent Data Monitoring Committee (iDMC) has been convened for this study for purposes of safety monitoring. The iDMC will meet at established intervals (as per the iDMC charter) throughout the study and will also convene as necessitated by data and/or safety reviews. The iDMC will not be tasked with any efficacy analyses.

5.6 Timing of Data Analyses

The database lock will occur after all subjects complete participation in the double-blind period of the study.

For the database lock, applicable EDC data will be locked to protect write access after the following preconditions are fulfilled:

- All records are entered in the database.
- All AE are coded to the satisfaction of the Chief Medical Officer.
- All medications are coded to the satisfaction of the Chief Medical Officer.

- All data queries have been resolved.
- All decisions have been made regarding all protocol violations and ITT population exclusions.
- Written authorizations to lock the database are obtained from Allakos Clinical Data Management and the Chief Medical Officer.

The randomization code for this study will not be revealed until the previous preconditions are fulfilled, and documentation of the database lock is complete. After the database lock, the randomization code will be made available to individuals at Allakos who are involved in the data analysis. Data analysis will commence after the data lock. In addition, the PK and ADA data may be locked and assessed separately.

5.7 Interim Analysis

No interim analysis will be conducted for this study.

5.8 Multicenter Study

The study will have approximately 70 sites in the US, Germany, and Poland. For efficacy analysis, sites within countries will be pooled together.

5.9 Multiple Comparisons/Multiplicity Adjustment

To control for the family-wise type-I error rate, the following testing procedures will be implemented:

Test primary efficacy endpoint at 2-sided α =0.05 level.

- If p≤0.05 for primary endpoint, then reject the null hypothesis that lirentelimab SC is no different from placebo SC and accept the alternative hypothesis that lirentelimab SC is superior to placebo SC in improving UAS7 score.
- If p≤0.05 for primary endpoint, the hypothesis tests for the secondary endpoints will proceed in the prespecified order (see Section 2.2). If at any point during the analysis of the secondary endpoints, the statistical test is not significant at 2-sided α=0.05 level, the hypothesis testing procedure will stop. Lirentelimab SC will be deemed superior to placebo SC for all endpoints prior to the stop.

5.10 Examination of Subgroups

Key endpoints will be summarized by subgroup to assess the consistency of the treatment effect across each of these subgroups. For any subgroup, if there are zero subjects within a stratification

stratum in any treatment group, the statistical model will not be adjusted by the stratification factors. Subgroups to be considered are:

- Sex (Male, Female)
- Age group ($<65, \geq 65$)
- Race (White, Non-White)
- Ethnicity (Hispanic or Latino, Not Hispanic or Latino)
- Region (U.S., non-U.S.)
- Baseline weekly itch severity score $(<13, \ge 13)$
- History of angioedema at screening (Yes, No)
- Prior omalizumab experience for the treatment of CSU (exposed, naïve)
- Baseline UAS7 score (16–27, 28–42)
- Duration of disease prior to baseline (<2, 2-10, >10 years)
- Screening IgE (\geq 43 kU/L, <43 kU/L)

6. Statistical Analysis

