3.2 Methods of Assigning Subjects to Treatment Groups

Approximately 130 subjects (65 per arm) will be randomized to treatment with lirentelimab SC or placebo SC in a 1:1 ratio. Stratified permuted block randomization will be used. Randomization will be stratified based on UAS7 score (16–27 vs. 28–42) and on Omalizumab experience for the treatment of CSU (omalizumab-exposed vs. omalizumab-naïve). An Interactive Response Technology System (IRT) will be used to perform the randomization.

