6.9 Analyses of Efficacy Endpoints

For all efficacy variables, the analysis will be comparison of lirentelimab SC and placebo SC groups. The following null and alternative hypotheses for the primary endpoint will be tested for lirentelimab SC group and placebo SC group:

H₀: No treatment difference between lirentelimab SC and placebo SC

H1: There is a treatment difference between lirentelimab SC and placebo SC

Omalizumab experience for the treatment of CSU (exposed, naïve) and UAS7 score (16–27, 28–42) will be the 2 stratification factors for subject randomization and will be accounted for in the statistical modeling for efficacy. In addition, if it is evident that the primary endpoint is confounded by baseline disease characteristics at study entry, then the primary efficacy analysis will be adjusted for the effects of these variables.

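### SAP 5.10 always drops both stratification factors in the omalizumab and UAS7 subgroups, although only the factor that defines the subgroup needs to go

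*SAP*

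**What the plan says.** SAP 5.10 sets one rule for all subgroup models, triggered when a subgroup has nobody in some "stratum in any treatment group, the statistical model will not be adjusted by the stratification factors". The consequence is all-or-nothing. There is no factor-by-factor removal and no exception for a subgroup that is itself defined by a stratification factor.

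The list in the same section includes omalizumab experience (exposed, naïve) and baseline UAS7 (16–27, 28–42). Under SAP 3.2 these are the two factors used in the stratified permuted-block randomization.

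Elsewhere the SAP commits to adjustment. Section 5.3: "Efficacy analyses will be adjusted for baseline values and randomization strata". Section 6.9, on the same two factors: they "will be the 2 stratification factors for subject randomization and will be accounted for in the statistical modeling for efficacy".

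The models differ by endpoint. The primary ANCOVA (6.9.1) has treatment, baseline UAS7 as a score, and omalizumab experience; its sample code adds region. The MMRM and the CMH test (6.9.2) carry both omalizumab experience and the UAS7 category.

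**The concern.** A fallback for an empty stratum is meant for sparse data. Where the subgroup variable is a stratification factor, the empty stratum comes from the definition of the subgroup and says nothing about sparsity. Only the factor that has become constant needs to leave the model. The rule as written also discards the other factor, by which subjects within that level were randomized.

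At stake is the quality of a descriptive check. These tables are meant to show whether the treatment effect is consistent across subgroups. Randomizing by a factor and then leaving it out of the analysis keeps the balance but overstates the standard error, for no gain. It also leaves 5.10 at odds with 5.3 and 6.9, which someone would have to settle at the programming stage.

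**Working it through.** **1. The plan's own figure.** The subgroup rule states no number. The nearest stated figure is power above 90% with 55 per arm, difference 8 and SD 11 (SAP 3.4). Power = Φ(8 / (11·√(2/55)) − 1.96) = Φ(3.81 − 1.96) = Φ(1.85), about 96.8%. It is reproduced, and the subgroup rule does not affect it.

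**2. When the rule fires.** Two binary factors give four strata.

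| Subgroup level | Strata empty by definition | Rule fires |
|---|---|---|
| Omalizumab exposed | both naïve strata | always |
| Omalizumab naïve | both exposed strata | always |
| UAS7 16–27 | both 28–42 strata | always |
| UAS7 28–42 | both 16–27 strata | always |

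This holds whether a stratum means one level of a factor or one of the four crossed cells.

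**3. What each model loses.**

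| Model | In omalizumab levels | In UAS7 levels |
|---|---|---|
| Primary ANCOVA | a constant only; baseline UAS7 score stays | omalizumab experience, normally estimable |
| MMRM | UAS7 category, normally estimable; continuous baseline stays | omalizumab experience |
| CMH | UAS7 category, normally estimable | omalizumab experience |

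Continuous baseline UAS7 is taken to stay because SAP 5.3 names baseline values separately from randomization strata.

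**4. Size in the UAS7 subgroups, primary ANCOVA.** Let p be the exposed share, g the difference in UAS7 change between exposed and naïve subjects, and s the residual SD with the term in the model. Leaving the term out adds p(1−p)g² to the residual variance, so the interval widens by √(1 + p(1−p)g²/s²). The documents give neither p nor g. Assumed: p from 20% to 40%, g of 4 or 6 points, and s of 10 or 11 (11 is the SAP's pooled SD).

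| p | g | p(1−p)g² | ratio, s = 10 | ratio, s = 11 |
|---|---|---|---|---|
| 0.20 | 4 | 2.56 | 1.013 | 1.011 |
| 0.20 | 6 | 5.76 | 1.028 | 1.024 |
| 0.40 | 4 | 3.84 | 1.019 | 1.016 |
| 0.40 | 6 | 8.64 | 1.042 | 1.035 |

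So the intervals are about 1% to 4% too wide. In points: if 55% of 130 subjects have UAS7 28–42 (assumed), that level has about 72 subjects, 36 per arm. With s = 10 the interval is about 2 × 2.0 × 10 × √(2/36) = 9.4 points wide, and the excess is about 0.1 to 0.4 points.

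**5. Bias.** Randomization is stratified on omalizumab experience within each UAS7 level, so the arms stay close on it: in simulated trials the mean between-arm difference in exposed share was about 2 percentage points. Its sign is random, and the root mean squared error (RMSE) of the estimate with and without the term differed by at most 0.01.

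**6. Small subgroups where a level is empty in one arm by chance.** Simulated trials of 130 subjects (true effect −8, residual SD 10, blocks of 4 assumed), 13-subject subgroups with an empty omalizumab-by-arm cell:

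| Exposed share, g | RMSE: dropped → kept | 95% CI width: dropped → kept |
|---|---|---|
| 20%, 4 | 6.3 → 6.8 | 26.9 → 29.2 |
| 30%, 6 | 6.7 → 6.9 | 27.2 → 30.0 |

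The direction was the same in all four combinations of 20% or 30% exposed and g of 4 or 6. When one arm has no exposed subjects, the added term leaves the other arm's exposed subjects contributing almost nothing to the treatment contrast. Dropping the factor is the more precise choice there.

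**The case against.** The strongest reply is that little turns on this. The subgroup tables listed in SAP Appendix 2 cover only change in UAS7 at Week 12. They are descriptive and outside the testing order in SAP 5.9. In the omalizumab levels the primary ANCOVA loses nothing of value. A specific rule in 5.10 may also be meant to override the general statements in 5.3 and 6.9. A lenient reading, counting only strata that can occur within the subgroup, would avoid the certain trigger.

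Most of this stands and sets the size of the point. But the SAP does not state the lenient reading. Nothing justifies an override in levels where the other factor is estimable. And 5.10 speaks of key endpoints without limiting itself to UAS7 change, so MMRM and CMH subgroup analyses are within its scope.

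A reader might infer more than the documents support:

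- *That subgroup estimates are biased.* An imbalance of 0.2 in exposed share times 3 to 6 points (assumed) does move a single estimate by 0.6 to 1.2 points. The trigger is symmetric between arms, however, and simulated bias was within 0.1 point. This is random error that the interval already reflects.
- *That the rule costs 11% to 14% in interval width in small subgroups.* A gain of that order comes from fitting one model to all subjects. With 30% exposed and g = 6, such a model gives a width of 24.2 without omalizumab and 23.5 with it, against 27.2 from the subgroup alone. Pooling assumes common slopes and variance, which is a separate trade-off.
- *That the fallback is wrong wherever it fires.* Step 6 shows the opposite for chance-empty cells in small subgroups.
- *That exposed and naïve subjects, or the two UAS7 categories, are compared under different models.* Both levels of each factor trigger, so both get the same model.

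**Conclusion.** The point holds in a narrow form. In the four subgroup levels defined by a randomization factor, SAP 5.10 as written always removes both factors where only one needs to go. For the primary endpoint, the consequence is loss of the omalizumab term in the two UAS7 subgroups, with intervals about 1% to 4% too wide. That range depends on the assumed exposed share (20% to 40%), the assumed prognostic difference (4 to 6 points) and a residual SD of 10 to 11. If exposure is not prognostic, the excess is nil. For MMRM and CMH, the UAS7 category would also be lost in the omalizumab levels, if those analyses are run by subgroup. There is no systematic bias and no effect on the primary test, its power or the type I error. This is a minor, free improvement that also removes a conflict with SAP 5.3 and 6.9.

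**What to change.** Add to SAP 5.10: 'When a subgroup is defined by a stratification factor, only that factor is omitted; the other stratification factor and the continuous baseline value stay in the model. The empty-stratum rule is applied only to the remaining factor.'

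Leave the existing fallback in place for small subgroups with a cell that is empty by chance.

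The cost is two sentences and a small programming change. In the UAS7 levels the ANCOVA spends one degree of freedom, which is negligible at the expected sizes. The change should be made before unblinding, so that the reading of the rule is not chosen with the results in view.
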